For adverse event reporting, all eyes of participants randomized to an intervention group after the baseline visit will be considered. Results will be expressed as the number of cases (eyes).

The final results report will be displayed in tables or graphs, as appropriate.

The investigational drug will be considered safe and tolerable when there are no clinical or statistical differences in all primary outcome variables compared to its comparators.

Subjects with an adherence rate greater than 60% will be included in the statistical analysis to meet the study objective, based on the subject's diary. However, even if the subject's diary indicates adherence greater than 60%, if the adherence calculated by weight is less than 30%, the subject will not be included. The minimum dose necessary to obtain a pharmacological effect (lubricant/1 gel application per day) and the presence of adverse events (exposure) were considered sufficient to meet the overall design objective, in accordance with the pharmacological characteristics of the investigational product.

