Eye Comfort Index (ICO) score.	The ICO is a questionnaire designed to measure irritation of the ocular surface, it assesses symptoms	The evaluator will apply the questionnaire to the subject and allow the subject to answer it calmly without any pressure and/or	Discrete quantitative.	
 Score: 0= None, 100 = High discomfort. 	
 - U for Mann-Whitney. - Wilcoxon Ranges.

Chondroitin Sulfate 0.18%/Sodium Hyaluronate 0.2%

	focused on the comfort associated with ocular surface alterations. Elevated values indicate more Severe.	coercion. See ICO Annex.			
Changes in visual capacity (CV)	Visual acuity (VA) is a test of visual function. Spatial VA is the ability to distinguish separate elements of an object and identify them as a whole. It is quantified as the minimum angle of separation (located at the nodal point of the eye) between two objects that allows them to be perceived as separate objects.	Snellen's Primer	Discrete quantitative.	Fraction, normal value = 20/20	
 - U for Mann-Whitney. - Wilcoxon Ranges.
Changes in tear film rupture time (LRT) with fluorescein.	The stability of the tear film is usually evaluated in the clinic by the TRL. It consists of instilling fluorescein on the ocular surface to allow the visualization of the tear film	It will be measured at the end of a blink and will be asked not to blink immediately until the tear film on the cornea is broken.	Continuous quantitative.	> 10 seconds.	
 - U for Mann-Whitney. - Wilcoxon Ranges.

Chondroitin Sulfate 0.18%/Sodium Hyaluronate 0.2%

	and measure the time it takes to break since the last blink.				
Changes in corneal and conjunctival staining with lysmine green.	Detection of epithelial defects in the conjunctiva and cornea.	Direct observation with slit lamp, Oxford scale graduation. See annex Oxford scale.	Ordinal Qualitative	
Degrees:
 
The staining is presented by a series of panels (A-E). Stain points range from 0-5 for each panel and 0-15 for the total exposed area of the conjunctiva and cornea.
	
 - Pearson's square chi or Fisher's exact. - McNemar test (if applicable).

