The data will be collected and sorted in an Excel spreadsheet (Microsoft® Office). The data will then be exported to the SPSS program platform. The variables will be categorized according to their nature (see [Table 2](#)).

Study participants will be identified by a number and their initials.

The initials of the study subject will be obtained starting with the first letter of the name, followed by the first letter of the first surname and the first letter of the second surname, obtaining a maximum of three letters, in case the person has two names or compound surname, the first letter will always be used.

Example:

To. [name]	B. [name]
to. Initials: AMC	b. Initials: JDO

Once the subject has been selected, they will be assigned a number with which they will be identified throughout the study. This code will be made up of eight numbers in the following order from left to right:

- Three digits of the molecule under study according to the name by the sponsor.
- Two digits corresponding to the research centre number.
- Three digits of the number following their inclusion assigned to the research centre.

The results of the continuous quantitative variables will be presented in measures of central tendency: mean, standard deviation and ranges, see [Table 2](#).

The Kolmogorov-Smirnov and Shapiro Wilk test will be performed to determine the type of distribution of the data (normality) in the results obtained in each study group. [5]

The statistical analysis of the continuous quantitative variables to find significant differences (p) will be as follows:

- Intra-group analysis: will be determined by Wilcoxon's rank test, for quantitative variables. [6]
- Inter-group analysis: Differences between groups will be analyzed using the Mann-Whitney U statistic.

The level of difference to consider significance will be an alpha (α) of 0.05 or less. A 95% CI will be considered for the non-inferiority criteria.

The result of the nominal and ordinal qualitative variables will be presented in frequencies, proportions and percentages, see [Table 2](#).

The statistical analysis to identify significant differences in the qualitative variables will be carried out by creating 2x2 contingency tables and will be carried out as follows:

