- Intra-group difference: McNemar test. This is applied to 2x2 contingency tables with a dichotomous feature, with pairs of paired subjects, to determine if the marginal frequencies of row and column are equal (marginal homogeneity).
- Difference between groups: Pearson's Chi-square (χ^2) test or Fisher's exact test at expected values less than 5.

The level of difference to consider significance (p) will be an alpha (α) of 0.05 or less.

Chondroitin Sulfate 0.18%/Sodium Hyaluronate 0.2%

For the reporting of adverse events, all eyes of those participants who were randomly assigned to an intervention group after PI instillation (ITT) will be considered.

The final report of the results will be shown in tables or graphs, as appropriate.

Those subjects who meet a minimum adherence of 60% will be included in the statistical analysis to meet the objective of the study, taken from the subject's diary. However, even if the subject's adherence is greater than 60% per diary, if the adherence calculated by weight is less than 30%, the subject will not be included.

The investigational drug will be considered safe and tolerable when there are no clinical and statistical differences in all primary outcome variables, with respect to its comparator (Artelac® Nighttime Gel).

Table 3. Triangulation of concepts

Variable Type	Variable	A1	B1	B2	C1	D1	E1	E2	E3	E4	E5	E6	E7	E8
Background														
A1	Demographic			DT										
Basal														
B1	Medical History		DT			T								
B2	Comprehensive ophthalmological evaluation		DT	DT		TB			TB		B	B		T
Safety														
C1	Incidence of AD			TB	TB		TB	TB	TB		TB	TB	TB	TB
Tolerability														
D1	ICO			DB			DB							
Secondary outcome														
E1	TRL			DB		TB		DB						
E2	Vitals			DB		TB			B					

Chondroitin Sulfate 0.18%/Sodium Hyaluronate 0.2%

E3	Posterior segment	DB	TB	B
E4	Quality Questionnaire			TB
E5	PIO	DB	TB	B
E6	Visual Ability	DB	TB	B
E7	Laboratory tests	DB	TB	B
E8	Ocular surface stains	TB	TB	TB

D. Descriptive Statistics; T, 2x2 contingency table; B, Bivariate Analysis; M, Multivariate Analysis.

Changes

1. First version of the document, no changes apply.

Author of the document

Ph.D. in Cs. [name].

Biostatistics.

Clinical Operations.

Laboratorios Sophia, S.A. de C.V.

[name]

[name]

References

<https://doi.org/10.1007/BF03163747>.

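### The between-arm test of the primary comfort index ignores the collected baseline and does not state final or change score; ordinal staining grades go into 2x2 tables with no cut-point

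*SAP*

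**What the plan says.** **Comfort index.** Protocol 6.4.1.1 and the SAP's outcome list make it the primary tolerability variable. The schedule (Protocol 6.5, SAP Table 1) places it at the baseline and final visits only. SAP Table 2 labels the row "Eye Comfort Index (ICO) score", while neighbouring rows are labelled as changes, for example "Changes in tear film rupture time (LRT) with fluorescein". The tests named for it are the Mann-Whitney U and "Wilcoxon Ranges".

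**SAP, Methods of Analysis.** Within arms: "Intra-group analysis: will be determined by Wilcoxon's rank test, for quantitative variables". Between arms: "Differences between groups will be analyzed using the Mann-Whitney U statistic". Normality tests are planned, but nothing is said to follow from them. One sentence ties a 95% CI to non-inferiority criteria; no margin is given.

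**Protocol.** The Summary and 8.3.1 name Kruskal-Wallis between groups. Section 8.3.1 then adds Student's t for quantitative variables.

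**Decision rule.** SAP: "The investigational drug will be considered safe and tolerable when there are no clinical and statistical differences in all primary outcome variables". Protocol 8.3.1 makes the condition that "there are no clinical or statistical differences in all primary outcome variables compared to its comparators".

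**Staining.** SAP Table 2 types it as ordinal, scored 0-5 per panel and 0-15 in total. It assigns Pearson's chi-square or Fisher's test between arms and McNemar's test within arms. The Methods text puts qualitative variables into 2x2 tables. The Oxford annexes of both documents define a single grade from 0 to V. No cut-point appears anywhere.

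**The concern.** The baseline comfort score is collected, yet it enters only the within-arm test. The comparison between arms, which is the one the decision rule needs, makes no use of it.

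The analysis variable is also left to inference. The word score, next to rows labelled as changes, suggests the final-visit score, but no sentence says so, and the protocol adds a second, different test. A final-score test and a change-score test are different analyses of the same data.

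Because the rule treats the absence of a difference as evidence of safety and tolerability, a less sensitive analysis makes the favourable conclusion easier to reach. The comfort index is one of only two primary variables, so an open choice here bears directly on that conclusion.

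For staining, collapsing an ordinal grade to two levels discards information, and with no cut-point fixed the result can depend on where the line is later drawn.

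**Working it through.** **The plan's own figure.** There is none for these tests. The sample size rests on a tolerance proportion: 26 subjects, and 26 × 1.2 = 31.2, rounded up to 32. This gives 16 per arm, or 26 / 2 = 13 per arm if the loss allowance is used up. Effect size, correlation ρ between baseline and final score, and floor are all assumptions below.

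**Why the choice of variable matters.** Relative to a final-score SD of 1, the residual SD is 1 for the final score, √(2(1−ρ)) for change and √(1−ρ²) with baseline adjustment. Under a normal approximation at 16 per arm and two-sided 0.05, the difference detectable with 80% power is (1.96 + 0.84) × SD × √(2/16):

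| ρ | Final | Change | Adjusted |
|---|---|---|---|
| 0.3 | 0.99 | 1.17 | 0.94 |
| 0.5 | 0.99 | 0.99 | 0.86 |
| 0.7 | 0.99 | 0.77 | 0.71 |

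Change is worse than the final score below ρ = 0.5 and better above it. The adjusted analysis is at least as good as either.

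**Simulation with rank tests.** Settings: 20,000 trials each, bivariate normal scores, 0.8 SD shift in the final score, two-sided 0.05. The floor version sets score = max(0, latent − c) with 80% of control scores at 0. Rank-ANCOVA regresses pooled final ranks on arm and pooled baseline ranks. Entries separated by slashes are for ρ = 0.3/0.5/0.7.

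| Scores | Per arm | Mann-Whitney, final score | Rank-ANCOVA | Gain, points |
|---|---|---|---|---|
| Normal | 16 | 56% | 59/66/81% | 3/10/25 |
| Normal | 13 | 48-49% | 50/57/70% | about 1 to 22 |
| 80% floor | 16 | 42-43% | 43/46/52% | about 1 to 10 |
| 80% floor | 13 | 36.3/35.3/36.1% | 36.1/37.1/43.5% | −0.2/1.8/7.4 |

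Mann-Whitney on change, normal scores, 16 per arm: 43/56/78%. Under the null the rank tests reject in 4-5% of trials.

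**Disagreement on significance, 16 per arm.** Final-score and change-score tests disagree in 33/35/38% of trials with normal scores and 24/25/27% with the 80% floor, at 0.8 SD. With no true difference they disagree in 7-9%. The rank test and Student's t on the final score disagree in 7% (normal) and 15-16% (80% floor) at 0.8 SD.

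**Staining, 16 per arm.** The grade distributions are assumed. The 2x2 tests are Pearson's, or Fisher's if any expected count is below 5.

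| Grades 0/I/II/III, arm v arm (%) | Mann-Whitney | Cut ≥I | Cut ≥II |
|---|---|---|---|
| 60/30/8/2 v 35/35/20/10 | 37.1% | 29.6% | 18.5% |
| 80/15/4/1 v 55/30/12/3 | 33.5% | 28.3% | 3.7% |
| 40/40/15/5 v 20/35/30/15 | 37.5% | 19.1% | 28.5% |
| 80/20 v 50/50 (0-I only) | 41.1% | 39.6% | n/a |

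In the three 0-III cases the two cut-points disagree on significance in 27-28% of trials.

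**The case against.** The strongest reply is that this is an exploratory Phase I trial, the Mann-Whitney U is a valid test, and baseline adjustment is a preference. Much of that stands. Healthy subjects make a floor likely, and there the gain is small: none at 13 per arm with ρ = 0.3. The 0.8 SD effect is also generous, because only the right eye is dosed while the questionnaire asks about both eyes.

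Second, the gap over final or change score is narrow. There is one post-baseline comfort score, and the row label points to it, so one sentence would settle the matter. That stands too, but the sentence is absent from both documents.

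Third, the documents agree more than they seem to. With two arms, Kruskal-Wallis is equivalent to the Mann-Whitney U apart from continuity correction, so the real conflict is the Student t sentence. A reader might infer from the normality tests that the SAP lets the data choose the test. It does not: it names the Mann-Whitney U without condition.

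Fourth, staining is secondary and outside the decision rule, and SAP Table 3 codes bivariate analysis beside the 2x2 table. If only grades 0 and I occur, the ordinal test gains little (41% v 40%). That limits the cost but leaves the score and the cut-point undefined.

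**Conclusion.** The point holds as a low-cost improvement. The collected baseline is unused between arms, the analysis variable is unstated, the protocol and SAP name different tests, and the staining score and its cut-point are undefined.

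The power gain from adjustment rests entirely on the assumed effect, correlation and floor, and ranges from nothing to about 25 points. The lack of a stated analysis variable is the firmer ground, because it holds in every setting examined.

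Three stronger readings are not supported. The planned test is not invalid or biased: it holds its level. The 24-38% disagreement is not a forecast for this trial: it applies at an assumed 0.8 SD, and the figure is 7-9% when the arms do not differ. The staining gap does not feed the safe-and-tolerable conclusion, which covers primary variables only. Nor would better efficiency repair a rule that takes non-significance as evidence of similarity; that needs a separate remedy.

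**What to change.** **(a) Comfort index.** In both documents name one between-arm test: rank-ANCOVA of the final-visit score on arm, with the baseline-visit score as covariate and no switch based on normality tests. Report the baseline-adjusted mean difference with its 95% CI, and state that the rank p-value governs the statistical part of the decision rule. If the Mann-Whitney U is kept instead, state that it is applied to the final-visit score.

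**(b) Alignment.** For this outcome, remove the Kruskal-Wallis and Student t wording from the protocol Summary and 8.3.1 so that the protocol matches the SAP. Delete or reconcile the SAP sentence on a 95% CI for non-inferiority, since no margin is stated.

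**(c) Staining.** State which score is analysed: per panel, total or single grade. Analyse it as ordinal, for the right eye at the final visit, separately for each dye: Mann-Whitney or the same rank-ANCOVA between arms, and Wilcoxon signed-rank within arm. Any 2x2 table kept needs a cut-point fixed in advance. Reconcile the carry-forward windows (10 days in the footnote to Protocol 6.5, 7 days in 6.5.1.2), which affect baseline staining but not the comfort index.

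**Cost.** Wording only: no new data, visits or subjects. Adjustment uses one degree of freedom. The rank p-value is not in score points, and at 16 per arm it disagrees on significance with the linear CI in 8-9% of simulated trials (normal) and 16-21% (80% floor). The text must therefore say which governs.

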
 
 I haven't felt it	0	1	2	3	4	5	Severe	
 
 							6	
 
							I haven't felt it	0	1	2	3	4	5	Severe								6
I haven't felt it	0	1	2	3	4	5	Severe															
							6															
2 In the past week, how often did your eyes feel gritty ?																						

 
 Never	0	1	2	3	4	5	Always	
 
 							6	
 
							Never	0	1	2	3	4	5	Always								6
Never	0	1	2	3	4	5	Always															
							6															
When your eyes felt gritty, typically, how intense was the sensation?																						

 
 I haven't felt it	0	1	2	3	4	5	Severe	
 
 							6	
 
							I haven't felt it	0	1	2	3	4	5	Severe								6
I haven't felt it	0	1	2	3	4	5	Severe															
							6															
3 In the past week, how often did your eyes feel throbbing ?																						

 
 Never	0	1	2	3	4	5	Always	
 
 							6	
 
							Never	0	1	2	3	4	5	Always								6
Never	0	1	2	3	4	5	Always															
							6															
When your eyes felt like they were stinging , how intense was the sensation usually?																						

 
 I haven't felt it	0	1	2	3	4	5	Severe	
 
 							6	
 
							I haven't felt it	0	1	2	3	4	5	Severe								6
I haven't felt it	0	1	2	3	4	5	Severe															
							6															
4 In the past week, how often did your eyes feel tired ?																						

 
 Never	0	1	2	3	4	5	Always	
 
 							6	
 
							Never	0	1	2	3	4	5	Always								6
Never	0	1	2	3	4	5	Always															
							6															
When your eyes felt tired , how intense was the feeling usually?																						

 
 I haven't felt it	0	1	2	3	4	5	Severe	
 
 							6	
 
							I haven't felt it	0	1	2	3	4	5	Severe								6
I haven't felt it	0	1	2	3	4	5	Severe															
							6															

5 In the past week, how often did your eyes feel sore ?

Never	0	1	2	3	4	5	Always	6
--------------	---	---	---	---	---	---	---------------	---

When your eyes felt sore, how severe was the sensation usually?

I haven't felt it	0	1	2	3	4	5	Severe	6
--------------------------	---	---	---	---	---	---	---------------	---

6 In the past week, how often did your eyes feel itchy ?

Never	0	1	2	3	4	5	Always	6
--------------	---	---	---	---	---	---	---------------	---

When your eyes felt itchy, how intense was the sensation usually?

I haven't felt it	0	1	2	3	4	5	Severe	6
--------------------------	---	---	---	---	---	---	---------------	---

Oxford Scale

PANEL	Grade	Criteria
A	0	Equal to or less than panel A
B	I	Equal to or less than panel B, greater than A
C	II	Equal to or less than panel C, greater than B
D	III	Equal to or less than panel D, greater than C
E	IV	Equal to or less than panel E, greater than D
>E	V	Greater than panel E
